4.3.3.2 Criteria to Resume Ipilimumab Dosing

Subjects may resume treatment with ipilimumab when drug-related AE(s) resolve(s) to Grade 1 or baseline value, with the following exceptions:

- Participants may resume treatment in the presence of Grade 2 fatigue.
- Participants who have not experienced a Grade 3 drug-related skin AE may resume treatment in the presence of Grade 2 skin toxicity.
- Participants with baseline Grade 1 AST/ALT or total bilirubin elevations who require dose delays for reasons other than a 2-grade shift in AST/ALT or total bilirubin may resume treatment in the presence of Grade 2 AST/ALT or total bilirubin.
- Participants with combined Grade 2 AST/ALT and total bilirubin values meeting discontinuation parameters (Section 4.3.4) should have treatment permanently discontinued.
- Drug-related pulmonary toxicity, diarrhea or colitis must have resolved to baseline before treatment is resumed. Subjects with persistent Grade 1 pneumonitis after completion of a steroid taper over at least 1 month may be eligible for retreatment if discussed with and approved by the PI.
- Participants who received systemic corticosteroids for management of any drug-related toxicity must be off corticosteroids or have tapered down to an equivalent dose of prednisone ≤ 10 mg/day.
- Subjects with Grade 1-3 drug-related endocrinopathies adequately controlled with only physiologic hormone replacement may resume treatment after consultation with the PI.
- Dose delay of ipilimumab which results in no ipilimumab dosing for > 12 weeks requires ipilimumab discontinuation, with exceptions as noted in Section 4.3.4. Although there is overlap among the discontinuation criteria, if discontinuation criteria are met for ipilimumab, but not for nivolumab, treatment with nivolumab may continue if ipilimumab is discontinued.

Ipilimumab may not be resumed sooner than 6 weeks (± 5 days) after the prior ipilimumab dose.

In general, participants who meet criteria to resume ipilimumab will also have met criteria to resume nivolumab, so it should be feasible to synchronize dosing of both drugs when resuming ipilimumab. In order to facilitate this, the dosing days of nivolumab and ipilimumab may be adjusted within the permitted ± 5 day window, as long as consecutive nivolumab doses are given at least 12 days apart.

One exception to note is when ipilimumab and nivolumab doses are delayed due to drug-related

Grade \geq 3 amylase or lipase abnormalities not associated with symptoms or clinical manifestations of pancreatitis. If the investigator assesses the Grade \geq 3 amylase or lipase abnormality to be related to ipilimumab and not related to nivolumab, nivolumab may be resumed when the amylase or lipase abnormality resolves to Grade $<$ 3 but ipilimumab may only be resumed when the amylase or lipase abnormality resolves to Grade 1 or baseline. Investigator attribution of this toxicity to the ipilimumab dosing must be clearly noted in the participant's medical chart. The PI should be consulted prior to resuming nivolumab in such participants.

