4.3.1. Dose Delay Criteria

Dose delay criteria apply to all drug-related AEs. Treatment delays are allowable up to 6 weeks for nivolumab and 12 weeks for ipilimumab from the last dose (any dose delays greater than this will require approval from the medical monitor).

Tumor assessments for all subjects should continue as per protocol **even if dosing is delayed**.

Nivolumab and ipilimumab administration should be delayed for the following:

- Grade 2 non-skin, drug-related adverse event, except for fatigue and laboratory abnormalities
- Grade 2 drug-related creatinine, AST, ALT and/or Total Bilirubin abnormalities
- Grade 3 skin, drug-related AE
- Grade 3 drug-related laboratory abnormality with the following exceptions:
 - Grade 3 lymphopenia or asymptomatic amylase or lipase elevation does not require dose delay
 - Grade ≥ 3 AST, ALT, Total Bilirubin will require dose discontinuation
 - Any AE, laboratory abnormality or intercurrent illness which, in the judgment of the investigator, warrants delaying the dose of study medication.

Participants who have drug-related toxicities that meet the criteria for dose delay should have both drugs (ipilimumab and nivolumab) delayed until retreatment criteria are met. (Exceptions apply to the retreatment criteria after dose delay of ipilimumab and nivolumab for Grade ≥ 3 amylase and lipase abnormalities that are not associated with symptoms or clinical manifestations of pancreatitis and that are attributed to ipilimumab alone.)

Rescheduling:

Nivolumab may be delayed until the next planned ipilimumab dose if the next ipilimumab dose is scheduled within the next 12 days. This will permit periodic ipilimumab dosing to be synchronized with nivolumab dosing.

Ipilimumab should be dosed at the specified interval regardless of any delays in intervening nivolumab doses. However, in order to maintain periodic synchronized dosing of ipilimumab and nivolumab, the dosing days of nivolumab (every 2 weeks ± 3 days) and ipilimumab (every 6 weeks ± 5 days) may be adjusted within the permitted ± 5 day window, as long as consecutive nivolumab doses are given at least 12 days apart. Ipilimumab may be delayed beyond the 5 day window if needed to synchronize with the next nivolumab dose.

If an ipilimumab dose is delayed beyond 6 weeks from the prior ipilimumab dose, then subsequent ipilimumab doses should be rescheduled to maintain the 6 week interval between consecutive ipilimumab doses.

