4.3.3. Criteria to Resume Dosing

4.3.3.1 Criteria to Resume Nivolumab Dosing

Subjects may resume treatment with nivolumab when the drug-related AE(s) resolve(s) to Grade \leq 1 or baseline, with the following exceptions:

- Subjects may resume treatment in the presence of Grade 2 fatigue.
- Subjects who have not experienced a Grade 3 drug-related skin AE may resume treatment in the presence of Grade 2 skin toxicity.
- For subjects with Grade 2 AST, ALT, or Total bilirubin elevations, dosing may resume when laboratory values return to baseline and management with corticosteroids, if needed, is complete.
- Subjects with combined Grade 2 AST/ALT AND total bilirubin values meeting discontinuation parameters (see package insert) should have treatment permanently discontinued.
- Drug-related pulmonary toxicity, diarrhea, or colitis must have resolved to baseline before treatment is resumed. Subjects with persistent Grade 1 pneumonitis after completion of a steroid taper over at least 1 month may be eligible for retreatment if discussed with and approved by the PI.
- Subjects with Grade 1-3 drug-related endocrinopathies adequately controlled with only physiologic hormone replacement may resume treatment after consultation with the PI
- Subjects who received systemic corticosteroids for management of any drug-related toxicity must be off corticosteroids or have tapered down to an equivalent dose of prednisone \leq 10 mg/day.
- Participants who delay study treatment due to any Grade \geq 3 amylase or lipase abnormality that is not associated with symptoms or clinical manifestations of pancreatitis, and that is assessed by the investigator to be related to ipilimumab and not to nivolumab, may resume nivolumab when the amylase or lipase abnormality has resolved to Grade < 3. The PI should be consulted prior to resuming nivolumab in such participants.
- Dose delay of nivolumab that results in treatment interruption of > 6 weeks requires treatment discontinuation, with exceptions as noted in Section 4.3.4.
- One exception to note is when ipilimumab and nivolumab doses are delayed due to drug-related Grade \geq 3 amylase or lipase abnormalities not associated with symptoms or clinical manifestations of pancreatitis. If the investigator assesses the Grade \geq 3 amylase or lipase abnormality to be related to ipilimumab and not related to nivolumab, nivolumab may be

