4.3.4.1. Nivolumab or Ipilimumab Dose Discontinuation

Treatment with nivolumab or ipilimumab must be permanently discontinued for any of the following:

- Any Grade 2 drug-related uveitis or eye pain or blurred vision that does not respond to topical therapy and does not improve to Grade 1 severity within the re-treatment period OR requires systemic treatment
- Any Grade 3 non-skin, drug-related adverse event lasting $>$ 7 days, or recurs with the following exceptions for laboratory abnormalities, diarrhea, drug-related uveitis, pneumonitis, bronchospasm, hypersensitivity reactions, infusion reactions, and endocrinopathies:
 - Grade 3 drug-related diarrhea, colitis, neurologic toxicity, uveitis, pneumonitis, bronchospasm, hypersensitivity reaction, or infusion reaction of any duration requires discontinuation
 - Grade 3 drug-related endocrinopathies, adequately controlled with only physiologic hormone replacement do not require discontinuation. Adrenal insufficiency requires discontinuation regardless of control with hormone replacement.
 - Grade 3 drug-related laboratory abnormalities do not require treatment discontinuation except:
 - Grade 3 drug-related thrombocytopenia $>$ 7 days or associated with bleeding requires discontinuation.
 - Any drug-related liver function test (LFT) abnormality that meets the following criteria require discontinuation:
 - Grade \geq 3 drug-related AST, ALT or Total Bilirubin requires discontinuation. In most cases of Grade 3 AST or ALT elevation, study drug(s) will be permanently discontinued. If the investigator determines a possible favorable benefit/risk ratio that warrants continuation of study drug(s), a discussion between the investigator and the PI must occur.
 - Concurrent AST or ALT $>$ 3 x ULN and total bilirubin $>$ 2x ULN
- Any Grade 4 drug-related adverse event or laboratory abnormality (including but not limited to creatinine, AST, ALT, or Total Bilirubin), except for the following events which do not require discontinuation:

- Grade 4 neutropenia \geq 7 days
- Grade 4 lymphopenia or leukopenia
- Isolated Grade 4 electrolyte imbalances/abnormalities that are not associated with clinical sequelae and are corrected with supplementation/appropriate management within 72 hours of their onset

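### The hepatic hold, restart and stop rules in Section 4.3 are not consistent between the two drugs or between sections, and need to be reconciled

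*Combined protocol and SAP*

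**What the plan says.** All references are to Section 4.3 of the combined protocol and SAP.

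- **Hold.** Section 4.3.1 lists "Grade 2 drug-related creatinine, AST, ALT and/or Total Bilirubin abnormalities" among the reasons to delay dosing, with no exception for values already raised at baseline. Patients who meet a delay criterion for a drug-related toxicity "should have both drugs (ipilimumab and nivolumab) delayed until retreatment criteria are met". The one exception named there concerns asymptomatic amylase and lipase abnormalities.
- **Nivolumab restart.** Section 4.3.3.1 has a general rule (resolution to Grade 1 or lower, or to baseline) and a stricter one for Grade 2 AST, ALT or bilirubin: "dosing may resume when laboratory values return to baseline and management with corticosteroids, if needed, is complete".
- **Ipilimumab restart.** Section 4.3.3.2 has a general rule (Grade 1 or baseline) and no matching Grade 2 hepatic rule. It has an exception instead: patients with Grade 1 liver tests at baseline, delayed for something other than a two-grade shift in those tests, "may resume treatment in the presence of Grade 2 AST/ALT or total bilirubin". The same section remarks that, in general, "participants who meet criteria to resume ipilimumab will also have met criteria to resume nivolumab".
- **Grade 3 stop.** Section 4.3.1 says that Grade 3 or higher "AST, ALT, Total Bilirubin will require dose discontinuation". The corresponding bullet in Section 4.3.4.1 opens with the same requirement and then continues: "In most cases of Grade 3 AST or ALT elevation, study drug(s) will be permanently discontinued". It goes on to provide for an investigator-PI discussion where continuing might be favourable.
- **Combined stop.** For combined Grade 2 AST/ALT and bilirubin, Section 4.3.3.1 speaks of patients "meeting discontinuation parameters (see package insert) should have treatment permanently discontinued". Section 4.3.3.2 makes the same provision but points to Section 4.3.4, within which Section 4.3.4.1 gives limits of AST or ALT above 3 x ULN together with total bilirubin above 2 x ULN.

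**The concern.** The delay rule treats the two drugs as a pair, but the restart rules then separate them for the same liver event without saying why. The stop rule for Grade 3 AST or ALT is worded both as absolute and as negotiable. Two investigators acting in good faith on different sections could hold, restart or stop treatment differently.

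That matters first for patient safety. It also matters for the secondary safety objective in Section 1.2, because treatment discontinuations would partly reflect which section was followed, and for how much of the combination patients receive. Raised baseline values are admitted by design: Section 3.1 allows AST and ALT up to 3 x ULN, or 5 x ULN with documented liver metastases.

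**Working it through.** No formula applies and the plan gives no figure to reproduce. The check sets the rules side by side.

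**Step 1: restart after a Grade 2 drug-related event, laboratory threshold only.**

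| Baseline | Course after the event | Nivolumab (4.3.3.1) | Ipilimumab (4.3.3.2) | Same answer? |
|---|---|---|---|---|
| Normal | Returns to normal | Met | Met | Yes |
| Normal | Settles at Grade 1 | Not met | Met | No |
| Grade 1 | Returns to Grade 1 | Met | Met | Yes |
| Grade 1 | Stays at Grade 2 | Not met | Depends on how the exception is read | Unclear |
| Grade 2 | At baseline | Met | Met | Yes |

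The steroid condition differs as well. For nivolumab after a Grade 2 liver event, steroid management must be complete. For ipilimumab, a taper to 10 mg/day or less of prednisone equivalent is enough.

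**Step 2: the exception for Grade 1 at baseline.** From Grade 1, a two-grade rise reaches Grade 3 (1 + 2 = 3), which Section 4.3.1 treats as discontinuation, not delay. A Grade 2 hepatic delay in such a patient is a one-grade shift (2 - 1 = 1), so read literally it falls within the exception. Ipilimumab could then restart at the level that triggered the hold. The other reading is that the exception concerns delays for some different toxicity, with Grade 2 liver values in the background that are not attributed to the drugs. Section 4.3.1 holds only for drug-related abnormalities, so on that reading there is no clash. The text does not choose between them.

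**Step 3: Grade 3 and above.**

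| Event | 4.3.1 | 4.3.4.1 |
|---|---|---|
| Grade 3 AST or ALT | Stop | Stop in the first sentence; then usual rather than invariable, with a route to continue |
| Grade 3 bilirubin | Stop | Stop |
| Grade 4 AST, ALT or bilirubin | Stop | Stop |

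The conflict is confined to Grade 3 AST and ALT. It lies within one bullet of Section 4.3.4.1 as well as between that bullet and Section 4.3.1. If treatment does continue, the default nivolumab rule applies on its face (Grade 1 or lower, or baseline). That is looser than the rule for the milder Grade 2 event, which requires baseline.

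**Step 4: what follows for a patient in the second row of Step 1.** Section 4.3.3.1 requires nivolumab to be discontinued after an interruption of more than 6 weeks, subject to the exceptions in Section 4.3.4.1 (prolonged steroid tapers, or non-drug-related reasons with PI approval). Section 4.3.4.1 also bars ipilimumab once nivolumab has been discontinued. A patient who satisfies the ipilimumab rule throughout could therefore lose both drugs.

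**Step 5: may ipilimumab be given while nivolumab is held?** The rescheduling text in Section 4.3.1 keeps ipilimumab on its own interval despite delays to intervening nivolumab doses, but it deals with scheduling. It does not settle the case where both drugs were held for one liver event and only one restart rule has been met.

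**The case against.** Several parts of the other side's case are sound.

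- **Drug-specific restart thresholds are not in themselves an error.** The instruction to hold both drugs could also mean that both sets of criteria must be met, so that the stricter governs. But the protocol does not say so. The separate restart it does spell out, for amylase and lipase, lets nivolumab go first. The hepatic difference runs the other way and is not explained.
- **The synchrony remark is hedged.** It describes what is generally so, and an exception does not contradict it. The hepatic rules sit badly with it and no more.
- **The Grade 3 line in Section 4.3.1 can be taken as a short pointer to the fuller rule in Section 4.3.4.1.** That would explain the difference between sections, but not the two wordings inside the Section 4.3.4.1 bullet.

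A reader might also infer stronger things that the documents do not support.

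- **That ipilimumab alone is authorised during active drug-induced hepatitis.** This needs the contested reading in Step 2. It also passes over the 6-week minimum interval, the steroid limit and the combined AST/ALT-bilirubin stop, and the event in question is a persistent Grade 2 elevation.
- **That no restart rule exists after a Grade 3 event.** The opening sentences of both resume sections are not limited by the grade of the original event.
- **That every Grade 2 or 3 liver event is affected.** Events that return to baseline, patients with Grade 2 at baseline, and Grade 3 bilirubin show no conflict in the laboratory threshold or stop rule.
- **That the package insert sets a different combined threshold.** The insert is not part of the documents. Two references show only that the source is not unique.

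**Conclusion.** The concern holds in four specific places:

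1. A patient with normal baseline values who settles at Grade 1 after a Grade 2 event meets the ipilimumab restart rule but not the nivolumab rule.
2. The exception for Grade 1 at baseline is at least ambiguous, and on one reading it permits ipilimumab at the grade that triggered the hold.
3. Grade 3 AST or ALT is both a mandatory stop and a usual one. The discretion does not reach bilirubin or Grade 4.
4. The combined AST/ALT-bilirubin stop is referred to two sources.

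The first and third follow directly from the current text. The second depends on which reading was intended, and the fourth is a matter of citation only. The number of patients affected cannot be derived, because the documents give no hepatic event rate and no distribution of baseline grades. The Simon design's sample size, significance level and power are unaffected. These are operative safety instructions, so correction is warranted even without a count. No view is taken here on which threshold or stop rule is right.

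**What to change.** Reconcile Sections 4.3.1, 4.3.3.1, 4.3.3.2 and 4.3.4.1 on AST, ALT and bilirubin. One hepatic table, with rows by baseline grade and event grade and columns for hold, restart and stop for each drug, would do it. The revision should:

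- state whether ipilimumab may be given while nivolumab is held for the same liver event;
- say which delays the exception for Grade 1 at baseline covers, and how it relates to the Grade 2 hold;
- use the same wording for Grade 3 AST/ALT throughout and, if continuation remains possible, state which restart rule then applies;
- cite one source for the combined AST/ALT-bilirubin threshold.

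The sponsor-investigator decides the content of each rule. The cost is a protocol wording amendment. Liver tests are already scheduled at every dosing visit (Sections 5.2 and 5.4), so no new assessments are needed, and the sample size does not change.

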4.3.4. Treatment Discontinuation Criteria

For all subjects, global deterioration of health status requiring discontinuation of treatment without objective evidence of disease progression at that time should be reported as 'symptomatic deterioration' in the source data. Every effort should be made to document objective progression (i.e., radiographic confirmation) even after discontinuation of treatment.

4.3.4.1. Nivolumab or Ipilimumab Dose Discontinuation

Treatment with nivolumab or ipilimumab must be permanently discontinued for any of the following:

- Any Grade 2 drug-related uveitis or eye pain or blurred vision that does not respond to topical therapy and does not improve to Grade 1 severity within the re-treatment period OR requires systemic treatment
- Any Grade 3 non-skin, drug-related adverse event lasting $>$ 7 days, or recurs with the following exceptions for laboratory abnormalities, diarrhea, drug-related uveitis, pneumonitis, bronchospasm, hypersensitivity reactions, infusion reactions, and endocrinopathies:
 - Grade 3 drug-related diarrhea, colitis, neurologic toxicity, uveitis, pneumonitis, bronchospasm, hypersensitivity reaction, or infusion reaction of any duration requires discontinuation
 - Grade 3 drug-related endocrinopathies, adequately controlled with only physiologic hormone replacement do not require discontinuation. Adrenal insufficiency requires discontinuation regardless of control with hormone replacement.
 - Grade 3 drug-related laboratory abnormalities do not require treatment discontinuation except:
 - Grade 3 drug-related thrombocytopenia $>$ 7 days or associated with bleeding requires discontinuation.
 - Any drug-related liver function test (LFT) abnormality that meets the following criteria require discontinuation:
 - Grade \geq 3 drug-related AST, ALT or Total Bilirubin requires discontinuation. In most cases of Grade 3 AST or ALT elevation, study drug(s) will be permanently discontinued. If the investigator determines a possible favorable benefit/risk ratio that warrants continuation of study drug(s), a discussion between the investigator and the PI must occur.
 - Concurrent AST or ALT $>$ 3 x ULN and total bilirubin $>$ 2x ULN
- Any Grade 4 drug-related adverse event or laboratory abnormality (including but not limited to creatinine, AST, ALT, or Total Bilirubin), except for the following events which do not require discontinuation:

- Grade 4 neutropenia \geq 7 days
- Grade 4 lymphopenia or leukopenia
- Isolated Grade 4 electrolyte imbalances/abnormalities that are not associated with clinical sequelae and are corrected with supplementation/appropriate management within 72 hours of their onset
- Grade 4 drug-related endocrinopathy adverse events, such as, hyper- or hypothyroidism, or glucose intolerance, which resolve or are adequately controlled with physiologic hormone replacement (corticosteroids, thyroid hormones) or glucose-controlling agents, respectively, may not require discontinuation after discussion with and approval from the PI.
- Any Grade \geq 2 drug-related pneumonitis or interstitial lung disease that does not resolve with dose delay and systemic steroids (also see package insert for Pulmonary Adverse Event Management)
- Any adverse event, laboratory abnormality, or intercurrent illness which, in the judgment of the Investigator, presents a substantial clinical risk to the subject with continued nivolumab/ipilimumab dosing.
- Any event that leads to delay in dosing lasting $>$ 6 weeks (or 12 weeks for ipilimumab) from the previous dose requires discontinuation, with the following exceptions:
 1. Dosing delays to allow for prolonged steroid tapers to manage drug-related adverse events are allowed.
 2. Dosing delays lasting $>$ 6 weeks (or 12 weeks for ipilimumab) from the previous dose that occur for non-drug-related reasons may be allowed if approved by the PI.
- In the case of pregnancy, the investigator must immediately notify the Sponsor or designee of this event. In most cases, the study drug will be permanently discontinued in an appropriate manner (eg, dose tapering if necessary for participant safety). Please contact the Sponsor or designee within 24 hours of awareness of the pregnancy. If the investigator determines a possible favorable benefit/risk ratio that warrants continuation of study drug, a discussion between the investigator and the PI must occur.

Prior to re-initiating treatment in a participant with a dosing delay lasting $>$ 6 weeks (or 12 weeks for ipilimumab), the PI must be consulted. Tumor assessments should continue as per protocol even if dosing is delayed. Periodic study visits to assess safety and laboratory studies should also continue every 6 weeks or more frequently if clinically indicated during such dosing delays.

The assessment for discontinuation of nivolumab should be made separately from the assessment made for discontinuation of ipilimumab. Although there is overlap among the discontinuation criteria, if discontinuation criteria are met for ipilimumab but not for nivolumab, treatment with nivolumab may continue if ipilimumab is discontinued.

If a participant meets criteria for discontinuation and investigator is unable to determine whether the event is related to both or one study drug, the participant should discontinue both nivolumab and ipilimumab and be taken off the treatment phase of the study. Continuation of ipilimumab after discontinuation of nivolumab is not allowed on study.

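### In section 4.3.4.1 the Grade 3 endocrinopathy exemption from permanent discontinuation is narrower than the Grade 4 exemption for glucose events and for events that resolve, and the resume rules do not match the Grade 4 exemption

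*Combined protocol and SAP*

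**What the plan says.** Section 4.3.4.1 sets the permanent stopping rules for both drugs.

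- **Grade 3 default.** The stop applies to "Any Grade 3 non-skin, drug-related adverse event lasting $>$ 7 days, or recurs with the following exceptions", followed by a list of exceptions.
- **Grade 3 endocrinopathy exception.** "Grade 3 drug-related endocrinopathies, adequately controlled with only physiologic hormone replacement do not require discontinuation". The next sentence adds: "Adrenal insufficiency requires discontinuation regardless of control with hormone replacement".
- **Grade 3 laboratory exception.** "Grade 3 drug-related laboratory abnormalities do not require treatment discontinuation except" for certain thrombocytopenia and liver-test findings.
- **Grade 4 default.** The stop applies to "Any Grade 4 drug-related adverse event or laboratory abnormality (including but not limited to creatinine, AST, ALT, or Total Bilirubin), except for the following events" on a short list.
- **Grade 4 endocrinopathy exception.** The list includes "Grade 4 drug-related endocrinopathy adverse events, such as, hyper- or hypothyroidism, or glucose intolerance". The condition set for this release is that the events are ones "which resolve or are adequately controlled with physiologic hormone replacement (corticosteroids, thyroid hormones) or glucose-controlling agents, respectively, may not require discontinuation". Continuation needs the principal investigator's approval.

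The resume rules are in 4.3.3.1 (nivolumab) and 4.3.3.2 (ipilimumab). Both start from a general rule that the event must have returned to Grade 1 (Grade 1 or lower for nivolumab) or baseline. Both then make the same endocrinopathy exception: "Subjects with Grade 1-3 drug-related endocrinopathies adequately controlled with only physiologic hormone replacement may resume treatment after consultation with the PI".

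**The concern.** The two exemptions sit in one section and deal with the same class of event, yet they define acceptable control differently. The Grade 3 bullet accepts hormone replacement alone. The Grade 4 bullet accepts hormone replacement, glucose-controlling agents or resolution. For some events the less severe grade therefore meets the stricter instruction. The resume bullets use the narrow Grade 3 definition and do not mention Grade 4, so they do not follow on from what the Grade 4 bullet permits.

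These are mandatory permanent stops in a trial planned for 50 patients (40 with primary and 10 with acquired resistance), and the safety profile is a secondary objective (section 1.2, item D). Who is stopped, how much drug they receive and how many discontinuations for toxicity are reported would depend on which bullet an investigator applies.

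**Working it through.** There is no figure to reproduce and no formula applies. The check sets the Grade 3 bullet, the Grade 4 bullet and the two resume bullets side by side.

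**Step 1: is a glucose-controlling agent a form of hormone replacement in this protocol?** The Grade 4 bullet gives corticosteroids and thyroid hormones as its hormone replacement and names glucose-controlling agents as a separate alternative. On the protocol's own wording the two are distinct, so the Grade 3 bullet does not cover glucose-controlling agents.

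**Step 2: compare the outcomes by grade.** The Grade 3 column assumes that the event lasts more than 7 days or recurs. It also assumes that an endocrinopathy outside the Grade 3 exception falls back to the default stop.

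| Drug-related endocrinopathy | Grade 3 | Grade 4 | Order |
|---|---|---|---|
| Non-adrenal, controlled by hormone replacement alone | No stop; stopping bullet asks for no approval | May continue with approval | As expected |
| Glucose intolerance controlled by glucose-controlling agents | Stop, unless classed as a laboratory abnormality | May continue with approval | Inverted |
| Resolves without hormone replacement (for example, hyperthyroidism) | Stop | May continue with approval | Inverted |
| Controlled but not resolved, by any other treatment | Stop | Stop | No inversion |
| Adrenal insufficiency on corticosteroid replacement | Stop regardless of control | Carve-out not repeated; corticosteroid replacement listed as a control | Not reconciled |

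**Step 3: which bullet governs a Grade 3 glucose event?** Section 4.3.4.1 lists laboratory abnormalities and endocrinopathies as separate Grade 3 exceptions. The Grade 4 bullet calls glucose intolerance an endocrinopathy. Glucose is also part of the routine chemistry panel in section 5.2, so the same event could be recorded as a laboratory abnormality and be exempt. The text gives no order of precedence.

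**Step 4: follow a permitted Grade 4 event into the resume rules, if dosing is held.**

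- If it resolves to Grade 1 or baseline, the general rule applies. There is no gap.
- If it is controlled but unresolved, the endocrinopathy bullets do not name Grade 4, and only the general rule is left. Until that rule is met, the patient waits.
- Section 4.3.4.1 requires discontinuation once the delay exceeds 6 weeks for nivolumab or 12 weeks for ipilimumab from the previous dose. Its exceptions are prolonged steroid tapers and approved delays for reasons unrelated to the drug. Neither plainly fits a drug-related endocrinopathy under stable control. The delay limit could therefore undo the exemption.

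**The case against.** The strongest reply is that the mismatch is narrow and that other text absorbs most of it.

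- **The general direction is as expected.** For a non-adrenal event on hormone replacement, Grade 3 is exempt outright and Grade 4 only with approval. This stands. A reader might infer that the endocrinopathy rules run backwards by grade throughout, and the documents do not support that. The inversion is confined to the two rows marked in the table.
- **Other treatments.** A reader might infer that any treatment short of hormone replacement is accepted at Grade 4. It is not: the bullet names only hormone replacement, glucose-controlling agents and resolution. This stands.
- **The laboratory exemption may cover Grade 3 glucose events.** It may, and the glucose case is conditional for that reason. It does not remove the problem, because one event can then be recorded in two ways with different outcomes. It also does not reach a clinical hyperthyroidism event.
- **The principal investigator's discretion resolves it.** That discretion is written into the Grade 4 bullet. The Grade 3 endocrinopathy bullet has none.
- **Stop and resume rules are compatible.** Being spared a permanent stop and having to wait for recovery can both be true. The Grade 1-3 limit in the resume bullets might also mean the grade at the time of redosing, which would let in a Grade 4 event that has improved on hormone replacement. Section 4.3.1 lets longer delays go to the medical monitor for approval. So it would be wrong to infer that Grade 4 events have no resume rule. What remains is the controlled but unresolved event, above all one held by glucose-controlling agents, which the resume bullets do not mention at any grade.

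**Conclusion.** The point holds in a limited form. Read literally, section 4.3.4.1 permanently stops two kinds of endocrinopathy at Grade 3 that may continue at Grade 4 with the principal investigator's approval: glucose intolerance controlled by glucose-controlling agents, if it is not classed as a laboratory abnormality, and an event that lasts beyond 7 days or recurs at Grade 3 and then resolves without hormone replacement. Separately, a Grade 4 event that is controlled but not resolved has only the general resume rule and could run into the 6- or 12-week delay limit.

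The conclusion rests on two readings: that glucose-controlling agents are not hormone replacement, which the Grade 4 bullet's own wording supports, and that a Grade 3 endocrinopathy outside its exception returns to the default stop.

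The number of patients affected cannot be derived. Table 2.2.1 gives an overall Grade 3-4 treatment-related rate (33% on the schedule used here) without separating endocrine events, and it would be wrong to apply that rate to them. Sample size, significance level and power are unaffected. What is exposed is consistent application of a mandatory stop, and with it exposure and the count of discontinuations for toxicity. Which rule is clinically right is not judged here.

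**What to change.** Amend the Grade 3 and Grade 4 endocrinopathy bullets in 4.3.4.1 and the endocrinopathy bullets in 4.3.3.1 and 4.3.3.2 together, so that:

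1. all four use one list of conditions and one definition of adequate control, stating whether glucose-controlling agents and resolution count;
2. the text says whether a glucose event falls under the endocrinopathy or the laboratory exemption;
3. the resume rules cover the same grades and forms of control that the stopping rules exempt;
4. the adrenal insufficiency carve-out, now stated only in the Grade 3 bullet, is reconciled with the Grade 4 bullet, which lists corticosteroid replacement.

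The clinical team decides which version applies in each case. The cost is a wording amendment to four bullets, with no extra patients, tests or visits.
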